### 6.2.1.3 Worst post baseline

Post baseline worst-case analysis visit will be created for DTBP and overall for parameters with defined abnormalities and/or toxicity grades to summarize values considered as the worst-case. For abnormalities, the worst-case is derived per parameter, and if both the lowest and highest values are considered abnormal, a participant can have 2 worst-case analysis visits for the same parameter. For toxicity grades, the worst-case is the value associated with the highest toxicity grade and is derived per parameter and toxicity direction (decreased/increased).

For deriving worst post baseline value all non missing values will be considered included unscheduled visits.

### 6.2.1.4 PK/PD analyses

Samples taken on or the day the day of occurrence of an important protocol deviation that may impact the interpretability of the PK/PD will be excluded from the PK/PD analysis. Important protocol deviations that may impact the interpretability of PK/PD will be flagged in the SDTM database prior to DBL.

## 6.2.2 Treatment Groups

The treatment group refers are defined in [Table 8](#).

**Table 8 Treatment Groups**

Treatment	Definition
ARGX-117 Dose Regimen 1 [REDACTED] [REDACTED]	[REDACTED] [REDACTED] [REDACTED]
ARGX-117 Dose Regimen 2 [REDACTED] [REDACTED]	[REDACTED] [REDACTED] [REDACTED]
ARGX-117 Dose Regimen 3 [REDACTED] [REDACTED]	[REDACTED] [REDACTED] [REDACTED] [REDACTED]
Placebo Cohort 1 (PBO C1)	Placebo received in cohort 1
Placebo Cohort 2 (PBO C2)	Placebo received in cohort 2
Total Placebo (Total PBO)	Placebo received in cohort 1 or 2

For the first interim analysis, 2 treatment groups will be displayed: ARGX-117 dose regimen 1 and Cohort 1 in the summary tables, figures and listings. For the second interim and final analysis, the following treatment groups will be presented depending on the decision of the EDRT:

- ARGX-117 Dose Regimen 1, ARGX-117 Dose Regimen 2 (option 1) and Placebo or,
- ARGX-117 Dose Regimen 1, ARGX-117 Dose Regimen 3 (option 2) and Placebo or,
- ARGX-117 Dose Regimen 1, ARGX-117 Dose Regimen 2 (option 3), ARGX-117 Dose Regimen 3 (option 3) and Placebo; [REDACTED] placebo groups will be combined for all analyses and not presented separately.

### 6.2.3 Definition of Baseline

**IVMP baseline:** The last available and first non missing value collected before or on Day 1 IVMP.

Assessments performed at Day 1 IVMP but without time information collected will be considered eligible to the IVMP baseline. In the case there are 2 assessments performed at Day 1 IVMP, and the time is missing for one of them, the assessment with time information collected will be assigned to IVMP baseline.

In addition, for HRPQ questionnaire, the questionnaire with at least one non missing item based on SDTM datasets for at least one item from HRPQ01 to HRPQ09 will be used for IVMP baseline.

**DBTP baseline (baseline):** The last available and non missing value collected before the first administration of IMP will be used as baseline. Assessments performed on the same day as the first IMP administration but without time information collected or with time information exactly equal to the time of first IMP administration and which are planned predose will be considered as predose. For pharmacodynamic assessments, assessments performed on the same day as the first IMP administration but without time information and which are planned predose will be considered as predose. Efficacy assessments (including questionnaires, grip strength, mMRC and 9-HPT) completed post administration on the day of the first administration of IMP will be considered in the baseline selection in the absence of pre administration assessments from that day.

In addition, for HRPQ questionnaire, the questionnaire date with at least one non missing item based on SDTM datasets for at least one item from HRPQ01 to HRPQ09 will be used for IVMP baseline. If not otherwise specified, the term baseline will be used to refer to DBTP baseline.

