**Double Blind Treatment Period (DBTP):**

- For the efficacy endpoints: From the first IMP administration date/time to V14 with 23:59 added as time part or date of early treatment discontinuation visit with 23:59 added as time part
- For AE and concomitant medication: From the first IMP administration date/time to:
  - Informed consent of LTE for participants who do enter into LTE. Date of informed consent corresponds to the treatment completion date in the main study. All data on the eCRF will be considered to belong to this period
  - 23h59 the day prior to the 1st FU visit at week 4 for those participants who do not enter into LTE or date of early study discontinuation with 23:59 added as time part if participant discontinued the study before FUV1
  - Date of study discontinuation with 23:59 added for participants who early discontinued study and do not enter in the safety follow up period

**DBTP and Safety Follow-up period:** For AE, from the first IMP administration date/time to:

- Informed consent of LTE for participants who do enter into LTE. Date of informed consent corresponds to the treatment completion/discontinuation date. All data on the eCRF will be considered to belong to this period
- Study discontinuation for those participants who do not enter into LTE

Participants who entered into LTE are participants who were eligible for LTE and signed the informed consent form.

**Study Day 1 IDVP:** The day of the first IVIg administration during IDVP

**Study Day 1 IVMP:** The day of the first IVIg administration during IVMP

**Study Day 1:** The day of the first administration of ARGX-117 or placebo

**Study Day 1 FU:** The day following V14/ED visit (D113) (for participants who do not enter into the LTE)

**End of Treatment Visit:** The V14 visit (D113) for participants who completed DBTP, or the visit following IMP discontinuation for participants who discontinue IMP prior to V14 (D113) or the last IMP administration date for participants who are on-going in the DBTP at the data cut-off date .

**End of Study Visit:** The V14 visit (D113) for participants entering the LTE, or the last recorded date in the DBTP or SFU period for participants not entering the LTE.

Scheduled or Unscheduled visits which do not fall into the visit windows will be listed, but not included in tables or graphs.

- **Conversion factors:**
  - 1 month = 30.4375 days
  - 1 year = 365.25 days
  - 1 week = 7 days
  - °C = (°F - 32)/1.8
- **Additional rules**

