**6.5.1.3 Grip strength (GS)**

Hand GS measurements consist of 3 repeated contractions with the right hand followed by 3 repeated contractions with the left hand. GS are assessed on-site at trial visits and monitored daily.

These analyses will be performed in the SAF set.

The variables computed by eCOA and used for the analyses are in detailed in section 6.2.1.1 and appendix 9.3. Analysis will be performed as defined in 6.2.1.2.

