**GS Daily Average**

The GS daily average will be derived for the most and less affected hand separately. If at least one value is missing for the most or less affected hand, the GS daily average will be considered as missing for the corresponding hand.

- Value, Change from baseline and percent change from baseline and maximal percent change of GS daily average

On the IVMP, actual value and change from IVMP baseline and percent change from baseline GS daily average will be summarized at last assessment for each hand (most affected and less affected).

On the DBTP, for each hand (most affected and less affected), the actual value and change from baseline and percent change from baseline GS daily average will be summarized at last assessments (as defined in 6.2.1.2).

For the computation of the percent change from baseline (either at IVMP baseline or DBTP baseline), in case of value of baseline equal to 0 for GS daily average, the value of baseline for the denominator will be imputed by 1.

[REDACTED]

- Net iAUC per week of the change from baseline of GS daily average

For each hand (most affected and less affected), net incremental AUC (net iAUC) of the change from baseline up to last assessment during DBTP will be derived using linear trapezoidal rule and standardized per week as follows:

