### Net iAUClast assessment per Week

*Net iAUClast assessment per week = [(iAUCday1-day2 + iAUCday2-day3 + ... + iAUCdn-1,dayn) / ((date of last assessment – date of randomization + 1)/7)], where n is the day of the last assessment of GS daily average.*

The calculation of net iAUClast assessment per week is detailed in appendix 9.4.

iAUC will be positive if there is an improvement of GS daily average measurements compared to baseline and negative otherwise. If a score is missing at a post baseline visit, the iAUC will be calculated from the last non missing available assessment up to the next non missing assessment.

Net iAUC per week will be displayed by treatment group and overall.

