### 9.3 eCOA

**Table 26 Derived Variables by eCOA**

Assessment	Endpoint	Derived in eCOA platform (Yes/No)	Derived in ADaM (Yes/No)
mMRC	mMRC-10 sum score	Yes	Yes
	Baseline mMRC-10 Sum Score	Yes	Yes
	mMRC-10 score decrease of at least 2 points compared to baseline	Yes	Yes
	mMRC-14 sum score	Yes	Yes
GS for each hand (most affected and less affected)	GS daily average	Yes	Yes
	GS 3 day moving average	Yes	Yes
	Baseline GS 3 day moving average	Yes	Yes
	% change from DBTP baseline on the GS 3 day moving average	Yes	Yes
	> 30% decrease met on the GS 3 day moving average compared to baseline	Yes	Yes
FSS	FSS total score	Yes	Yes
CAP-PRI	CAP-PRI total score	Yes	Yes

■ [REDACTED]

[REDACTED]

[REDACTED]

[REDACTED]

\_\_\_\_\_

[illegible]

CRS-BS-TP-000005 V 2.0

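### Net iAUC of the daily grip-strength average subtracts one single-day baseline from every post-dose day, an avoidable loss of precision in a descriptive secondary endpoint

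*SAP*

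**What the plan says.** Section 6.2.3 of the SAP defines the double-blind baseline once for all variables: "The last available and non missing value collected before the first administration of IMP will be used as baseline". Its one provision that names grip strength concerns timing, not averaging: "Efficacy assessments (including questionnaires, grip strength, mMRC and 9-HPT) completed post administration on the day of the first administration of IMP" may serve when that day has no pre-dose assessment. Either way the baseline is one day.

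Section 6.5.1.3 says what one reading is: "Hand GS measurements consist of 3 repeated contractions with the right hand followed by 3 repeated contractions with the left hand". On frequency it says: "GS are assessed on-site at trial visits and monitored daily". Footnote u of Table 18 starts daily monitoring in the IVIg dependency or monitoring period, so several pre-dose days exist for each participant.

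For each hand, "net incremental AUC (net iAUC) of the change from baseline up to last assessment during DBTP will be derived using linear trapezoidal rule". The sum runs over daily intervals, "where n is the day of the last assessment of GS daily average", and is divided by the number of weeks from randomization. Section 5.2 puts the end of treatment at "The V14 visit (D113) for participants who completed DBTP". Partial versions run from Day 1 to weeks 4, 8, 12 and 16. Participants below 8 kPa at baseline are excluded.

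Table 26 lists a separate variable, "Baseline GS 3 day moving average", derived both in the eCOA platform and in ADaM. It belongs to the 3-day moving average. Net iAUC has no 3-day version, and Table 24 lists only a descriptive summary of it (output 14.2.1.30).

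**The concern.** A last-value rule suits a measure taken at visits. Here the measure is daily, and the endpoint averages about 112 post-dose days. Averaging removes nearly all day-to-day error from the post-dose side, while the subtracted term keeps the full error of one day. An unusually good or bad Day 1 shifts a participant's whole curve.

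Section 6.2.1 provides an SE and 95% CI for efficacy measures, and Section 6.2.1.2 compares each active group with the placebo group of its own cohort. A 2:1 allocation of 24 gives 16 v 8. The extra noise goes straight into those intervals, and no listed model for net iAUC reduces it. The same single day also decides who falls under the 8 kPa exclusion.

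**Working it through.** The SAP states no figure on this point, so there is none to reproduce.

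**Inputs from the SAP.** Trapezoid over Days 1 to 113; divisor 113/7 = 16.14 weeks; Day 1 reading as baseline; 16 v 8 per cohort.

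**Assumed.** Day-to-day error SD s (it cancels from the shares); lag-one autocorrelation ρ from 0 to 0.9 (AR(1)); between-person SD of the true mean change t = 0.5s, s or 2s.

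**1. Share due to the baseline day (ρ = 0).** Trapezoid weights are ½ on Days 1 and 113 and 1 between.
- Net weight on the baseline day: ½ − 112 = −111.5, which contributes 111.5² = 12,432.25.
- Later days contribute 111 × 1² + ½² = 111.25.
- Share: 12,432.25 / 12,543.5 = 99.1%. Treating the endpoint as a plain mean of 112 days gives 112/113, also 99.1%.
- A simulation of 50,000 participants gave a squared correlation of 0.991 between baseline-day error and net iAUC error.

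**2. Sensitivity of the share,** as baseline/(baseline + post-dose):

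| Scenario | Share |
|---|---|
| ρ = 0.3 / 0.5 / 0.7 / 0.9, to Day 113 | 98.4% / 97.4% / 95.3% / 86.5% |
| Half of the days missing, ρ = 0 | 98.2% |
| Weekly readings only, ρ = 0 | 94.0% |
| Partial iAUC to week 4 / 8 / 12, ρ = 0 | 96.5% / 98.2% / 98.8% |
| Partial iAUC to week 4, ρ = 0.9 | 68% |

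**3. Error SD of net iAUC per week (ρ = 0).**
- One-day baseline: √(12,543.5) / 16.14 = 6.94s.
- Three-day baseline: the two earlier days each carry 112/3 and Day 1 carries ½ − 112/3, so the sum is 2 × 37.33² + 36.83² + 111.25 ≈ 4,255, and √4,255 / 16.14 = 4.04s.
- Error variance falls to 34% of the one-day value. It falls to 62% at ρ = 0.5, and only to 93% at ρ = 0.9.

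**4. Effect on the confidence interval.** For ρ = 0 the width ratio, one-day over three-day, is √{[t² + s²(1 + 1/112)] / [t² + s²(1/3 + 1/112)]}:
- t = 0.5s: √(1.2589/0.5923) = 1.46
- t = s: √(2.0089/1.3423) = 1.22
- t = 2s: √(5.0089/4.3423) = 1.07

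With ρ = 0.5 the error variances, in units of s², are about 1.01 and 0.63. The ratios are then 1.20, 1.11 and 1.04 (simulation: 1.19, 1.11, 1.04). At t = s and ρ = 0, the SE of the 16 v 8 difference is 0.610t with one day and 0.500t with three. The variance ratio of 2.0089/1.3423 = 1.50 is equivalent to needing 1.5 times the participants.

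**5. Change at last assessment, for contrast.** Section 5.5 limits GS endpoints other than net iAUC to last-assessment derived visits, so one day is compared with one day. With independent days the ratio is √[(t² + 2s²)/(t² + 4s²/3)] = √(2.25/1.583), √(3/2.333), √(6/5.333) = 1.19, 1.13, 1.06.

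**The case against.** Several objections carry weight.

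- **This is a choice, not an error.** The rule is clear and applies alike to all arms, so it does not bias the comparison. No formal testing is planned. That stands, and limits the point to precision.
- **A smoothed analysis already exists.** The 3-day moving average has its own baseline, change, percent change, ANCOVA outputs (14.2.1.36 and 14.2.1.37) and the >30% decline endpoint, and Section 6.5.5 uses it in the efficacy summaries. This stands for those endpoints, but net iAUC has no such counterpart.
- **The size rests on assumed SDs.** True. At t = 4s and ρ = 0 the excess is √(17.0089/16.3423) = 1.02, or 2%. Strong persistence also leaves a 3-day mean little to gain.
- **A change now is late.** The modification history of SAP v3.0 speaks of limits that were missing for interim analysis 2, so this version postdates that analysis. Section 2.1 unblinds cohort 1 at the first interim and all of cohort 2 at the second. The change must therefore be disclosed as post-unblinding.
- **Redaction.** Appendix 9.4, which details the iAUC calculation, and parts of 6.2.1.2 and 6.5.1.3 are blacked out. A GS-specific baseline or an adjusted model there cannot be excluded.

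A reader might infer that the 46%, 22% and 7% also describe change, percent change and the ANCOVA of the GS daily average. The documents do not support this: those endpoints use a single-day last assessment (step 5), so half or more of their measurement error remains whichever baseline is used.

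**Conclusion.** On the visible text the point holds for net iAUC and partial net iAUC of the GS daily average, and for those only. One day supplies about 99% of the 16-week measurement-error variance if daily errors are independent, at least 95% up to autocorrelation 0.7, and about 86% at 0.9.

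This is a share of measurement error. A reader might take it as a share of total variance, but true differences between participants may dominate, and the SAP gives no SD to settle this. The cost in interval width over a 3-day baseline runs from 46% down to 4% across the assumed t and ρ of 0 or 0.5, and falls further if true change varies more or errors persist more. It is a worthwhile, inexpensive improvement to a descriptive secondary endpoint in an exploratory trial, not a flaw that invalidates it.

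**What to change.** In Section 6.5.1.3, with a pointer from 6.2.3, compute net iAUC and partial net iAUC of the GS daily average against the mean of the GS daily averages over the last 3 days up to and including the pre-dose Day 1 reading. This is the baseline already derived for the 3-day moving average. Also:

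- State a minimum number of non-missing days. The moving average uses whatever days are available, so it can itself rest on one day.
- State which baseline the 8 kPa exclusion uses, since a new one could change who is analysed.
- Record the change in Section 7 as made after interim unblinding, and show the single-day-baseline result alongside.
- If Appendix 9.4 already sets a GS-specific baseline, make 6.2.3 refer to it instead.

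The cost is SAP wording and one additional result per iAUC endpoint; the variable exists in ADaM. The baseline reaches back two more days, still within the 7 days between the final IVIg day and V1 (note to Table 19). Values will differ slightly from earlier interim tables.

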### GS 3 day moving average (day-2, day-1, day 0)

GS 3 day moving average will be derived for each hand (most affected and less affected). GS moving average will be derived from the third day after the first GS daily average assessment. In case of missing value of GS daily average, GS 3 day moving average will be calculated based on the number of non-missing GS daily average values.

- Value, Change from baseline, percent change from baseline of 3-day GS moving average

On the IVMP, the actual value and change from baseline and percent change from IVMP baseline GS 3-day moving average will be summarized at last assessment for each hand (most affected and less affected).

On the DBTP, for each hand (most affected and less affected), the actual value and change from baseline and percent change from baseline GS 3 day moving average will be summarized at last assessments (as defined in 6.2.1.2). For the computation of the percent change from baseline (either at IVMP baseline or DBTP baseline), in case of value of baseline equal to 0 for GS 3-day moving average, the value of baseline for the denominator will be imputed by 1.

[REDACTED]  
[REDACTED]  
[REDACTED]  
[REDACTED]  
[REDACTED]  
I [REDACTED]  
[REDACTED]  
I [REDACTED]  
[REDACTED]

- Proportion of participants with a decrease of more than 30% from baseline over 2 consecutive days of GS 3-day moving average

For each hand (most affected and less affected), the parameter will be derived.

The date of the decrease of more than 30% from baseline over 2 consecutive days will be set as the first of the 2 days consecutive reduction of GS 3-day moving average .

The proportion of participants with a GS 3 day moving average decrease of more than 30% from baseline over 2 consecutive days of GS 3-day moving average during the following period of time:

- Start of IMP and last non missing GS 3 day moving average assessment during DBTP  
- Start of IMP and last non missing GS 3 day moving average assessment before IVIg retreatment  
will be summarized by treatment group and overall using descriptive analysis.

GS 3-day moving average data for IVMP baseline, last assessment during IVMP, baseline, last assessment during DBTP and last assessment before IVIg will be listed.

Participants who have a value of 0 at baseline will be excluded from the analysis.

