### 6.5.2 Functional Ability, Arm and Hand Function, Quality of Life, and Fatigue

**MMN-RODS®**

MMN-RODS© is a questionnaire to capture activity limitations specifically in participants with MMN. It consists of 25 items that are scored as follows: 0: Unable to perform, 1: Able to perform, but with difficulty and 2: Able to perform without difficulty.

MMN-RODS will be analyzed in the SAF set, using the centile metric.

The total raw score will be calculated by summing the raw score of each item (range 0-50). If at least one item has a missing value, the total raw score will be considered as missing.

The total raw score will be transformed into a centile metric score as described in appendix 9.5. The centile metric score ranges from 0 (most severe activity and social participations limitations) to 100 (no activity and no social participation limitations).

On the IVMP, actual values and change from baseline of MMN-RODS score, using the total raw score and the centile metric will be summarized by visit.

On the DBTP, actual values and change from baseline of MMN-RODS score, using the total raw score and the centile metric will be summarized by visit (as defined in 6.2.1.2).

[REDACTED]

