### 6.6.2 Pharmacodynamics Evaluation

Free C2 (mg/L), total C2 (mg/L) and CH50 (Eq/mL) concentrations will be assessed. PD evaluations will be performed based on the PD set

- The actual value, change from baseline, percent change from baseline or each cohort, each day and time point will be summarized using descriptive statistics on IVMP and DBTP on the PD set.

For DBTP only:

- For Free C2, CH50 and Total C2, the maximum percent change from Baseline will be displayed
- Free C2 and CH50, the maximum decrease from baseline and minimum postbaseline value will be derived during DBTP.
- For Total C2, the maximum increase from baseline and maximum postbaseline value will be derived.

For deriving maximum decrease from baseline, minimum post baseline value, maximum increase and maximum postbaseline value all postbaseline nonmissing values will be considered included unscheduled visits.

- PD values expressed as below the quantification limit will be imputed by the value of the quantification limit itself. The LLOQ for Free C2, CH50 and Total C2 are 0.049 mg/L, 0 Eq/mL and 0.78 mg/L respectively.
- PD values expressed as above the quantification limit will be imputed by maximum value of PD parameter or ULOQ itself, if available.

For participants with a baseline PD value below/above the quantification limit, the PD parameter will be excluded from the statistical analysis involving change and percent change from baseline. Listings will always show the non imputed values

- When more than half (>50%) of the values at a single time point are BLQ, the mean, median and minimum values are reported BLQ. The SD, standard error (SE) and CV% are not calculated either. Maximum values are reported as observed.

Any potential impact of missing PD data or exclusion of the parameters from statistical analysis will be evaluated more closely during the data review process. Deviations from the presented calculation methods and data handling rules can be made, based on the discretion of the responsible PK/PD scientist and must be fully justified and documented.

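### Several IVIg-monitoring-period summaries say only baseline, which the plan defines as the later DBTP baseline, so read literally they use the wrong reference value

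*SAP*

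**What the plan says.** SAP Section 6.2.3 defines two reference values.

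- IVMP baseline: "The last available and first non missing value collected before or on Day 1 IVMP".
- DBTP baseline: "The last available and non missing value collected before the first administration of IMP will be used as baseline". A post-dose efficacy value from the first dosing day "will be considered in the baseline selection in the absence of pre administration assessments from that day".

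The section closes with the default: "If not otherwise specified, the term baseline will be used to refer to DBTP baseline". Section 5.2 defines change as the value minus baseline, and percent change as that difference divided by baseline, times 100.

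The IVMP sentences at issue are these.

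- MMN-RODS (6.5.2): "On the IVMP, actual values and change from baseline of MMN-RODS score, using the total raw score and the centile metric".
- GS daily average (6.5.1.3): "On the IVMP, actual value and change from IVMP baseline and percent change from baseline GS daily average".
- GS 3-day moving average (6.5.1.3): "On the IVMP, the actual value and change from baseline and percent change from IVMP baseline GS 3-day moving average".
- PD (6.6.2): one bullet covers value, change and percent change from baseline for both periods; each "time point will be summarized using descriptive statistics on IVMP and DBTP on the PD set".

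The IVMP sentences for mMRC-14 (6.5.1.2), 9-HPT, EQ-5D VAS, CAP-PRI and FSS (all 6.5.2) name the IVMP baseline.

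**The concern.** The default clause is sound in itself. The trouble lies in the sentences that rely on it while describing a period that ends before the DBTP baseline is fixed. Because the plan names the IVMP baseline for most endpoints, a programmer cannot treat the missing qualifier as house style. The two GS sentences even attach it to opposite measures: the absolute change for the daily average, the percent change for the moving average.

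If the text is followed as written, absolute and percent change in one GS table have different reference values, and the MMN-RODS and PD changes during IVIg treatment are measured backwards from a later value. IVMP and DBTP results share tables (14.2.1.26, 14.2.1.34, 14.2.1.41 to 14.2.1.43, 14.2.3.1, 14.2.3.3 and 14.2.3.5), and nothing in their titles would show a reader which reference applies.

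**Working it through.** The plan gives no figure to reproduce. The check applies the Section 5.2 formulas to the Section 6.2.3 definitions. All scores below are illustrative and do not come from the SAP.

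**1. Timing.** The schedule of activities (Table 18) puts IMV1 on day 1 and IMV3 on day 29, 43, 57 or 71 for IVIg every 2, 3, 4 or 5 weeks. V1 is 7 days after the final IVIg day (Table 19 notes), so nominally on IVMP day 36, 50, 64 or 78. V1 therefore falls 35, 49, 63 or 77 days after IMV1, that is 5 to 11 weeks. IMV assessments are made before IVIg, at the end of a cycle (Table 18 notes). The V1 value is taken one week into a cycle.

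**2. Grip strength at the last IVMP assessment.**
- Section 5.2 ends the IVMP one minute before the first IMP administration.
- Section 6.2.1.2 takes the last non-missing value in that period.
- Section 6.2.3 takes the last non-missing value before first IMP as DBTP baseline.

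These are normally the same measurement. Take 40 kPa at IVMP baseline and 48 kPa at that measurement:

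| Measure | Absolute change, as written | Percent change, as written | From IVMP baseline throughout |
|---|---|---|---|
| Daily average | 48 − 40 = +8 kPa (IVMP named) | (48 − 48)/48 = 0% (unqualified) | +8 kPa, 8/40 = +20% |
| 3-day moving average | 48 − 48 = 0 kPa (unqualified) | (48 − 40)/40 = +20% (IVMP named) | +8 kPa, +20% |

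The exception is a participant whose DBTP baseline is a post-dose day-1 value.

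**3. MMN-RODS, steady rise.** Take 70 at IMV1, 72 at IMV3 and 75 at V1.
- From IVMP baseline: 70 − 70 = 0 and 72 − 70 = +2.
- As written: 70 − 75 = −5 and 72 − 75 = −3.

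The starting visit shows a change, and the rise appears as negative values.

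**4. The same calculation on a path with a dip.** Take 50, 46 and 48 at IMV1 to IMV3 and 51 at V1.
- From IVMP baseline: 46 − 50 = −4 and 48 − 50 = −2 at IMV2 and IMV3.
- As written: 46 − 51 = −5 and 48 − 51 = −3.

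Here the sign does not flip. In general the two versions have opposite signs at IMV2 or IMV3 only when that visit's value lies between the IMV1 and V1 values. In simulation this occurred in about 33% of cases when the four values were independent noise and about 50% when they followed a random walk. Both models are assumptions.

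**5. MMN-RODS and PD at IMV3.** These are not forced to zero. Section 5.5 uses the value closest to the target day, and the IMV3 target is nominally 7 days before V1. Zero by construction would need one value to serve as both.

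**The case against.** The strongest reply is that the intent can be recovered. Section 6.2.3 defines an IVMP baseline for this purpose, and most endpoints use it. For both GS measures, Section 6.5.1.3 gives a zero-denominator rule for percent change that expressly covers either baseline. That suggests the IVMP baseline was intended for percent change on the IVMP, including the daily-average one. The rule does not reach the moving-average absolute change, although the paired measure in that sentence names the IVMP baseline. MMN-RODS and PD have no comparable cue. For PD, a single pre-IMP reference for both periods is a possible choice, but the plan does not state it.

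The consequence is also limited. Actual values are summarised beside every affected change, and the GS listings show the IVMP baseline, the last IVMP assessment and the DBTP baseline. The trial has no formal hypothesis testing. This argument stands, and it bounds the point.

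A reader might infer that all these IVMP changes are reversed in sign or zero by construction. The documents do not support that. Zero by construction applies to one GS measure in each sentence, with the day-1 exception. Exact reversal applies at IMV1, where the value there minus V1 is the negative of the whole IVMP change if IMV1 supplies the IVMP baseline. At IMV2 and IMV3 the sign depends on the path.

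**Conclusion.** The point holds as a wording error with a definite effect on the affected tables if the text is followed. Four sets of IVMP summaries default to a later reference value: MMN-RODS change, GS daily-average percent change, GS moving-average absolute change, and PD change and percent change. For GS, the unqualified measure is normally 0 at the last IVMP assessment. For MMN-RODS and PD, the starting visit generally shows a non-zero change, and IMV2 and IMV3 show an offset of either sign.

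This assumes that the programmer applies the Section 6.2.3 default literally and that the last IVMP grip-strength value is also the DBTP baseline. A reader might also infer that the efficacy comparisons are compromised. They are not: DBTP changes and treatment comparisons use the DBTP baseline as intended, and only descriptive pre-treatment summaries are touched. It should be corrected, but it does not threaten the trial's conclusions.

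**What to change.** 1. Keep the default clause in Section 6.2.3 and add that any change or percent change summarised on the IVMP is from IVMP baseline.
2. In Section 6.5.1.3, write IVMP baseline for both the absolute and the percent change in the IVMP sentences for GS daily average and GS 3-day moving average.
3. In Section 6.5.2, write IVMP baseline in the MMN-RODS sentence for the IVMP.
4. In Section 6.6.2, split the bullet so that IVMP PD changes are from IVMP baseline and DBTP changes from DBTP baseline, or state explicitly that a single pre-IMP reference is intended for both.

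The PD rule that excludes baselines beyond the quantification limit need not change for this point. The cost is SAP wording only: the IVMP baseline is already defined and is used for the other endpoints. If affected tables have already been run at an interim analysis, a check of which reference the programs used would settle whether any need to be reissued.
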